1.3. Rationale for the Study

Hidradenitis suppurativa (HS), also called acne inversa, is a chronic inflammatory skin disease characterized by inflammatory nodule, abscess, sinus and fistula formation, and scarring of the skin, most commonly in apocrine gland rich areas such as the axilla, inframammary area, inguinal area, perineum, and perianal area. In its moderate and severe forms, HS is debilitating and causes significant discomfort, pain, anxiety and depression, as well as impairment of quality of life. The exact cause of HS has not been identified, although genetic defects in the gene encoding for gamma-secretase have been described in subjects with HS. Potential target proteins include Notch, E-cadherin, and nicastrin. Notch plays an important role in hair follicle development, and a defect in Notch may lead to formation of epidermal cysts, dysregulation of normal T-cell mediated immune responses, and suppression of Toll-like receptor-4-induced pro-inflammatory macrophage mediated cytokine responses ([Radtke et al, 2010](#); [Wang et al, 2010](#)). Smoking and obesity have been associated with HS ([Prens and Deckers, 2015](#)).

Therapy for subjects with HS includes local and systemic antibiotics, pain medication, and anti-TNF- α agents such as adalimumab. Acitretin is used in early stage disease. Other drugs such as cyclosporin A, dapsone, and isotretinoin have been used with limited success ([Napolitano et al, 2017](#)). In more advanced cases, a multifaceted approach may be adopted, where surgical therapy is used to remove the chronic components of HS which are not expected to respond to medical therapy (e.g., scarring, fistulas, and sinus tracts), and long-term systemic medical therapy is used to treat the acute or sub-chronic manifestations of HS (e.g., abscesses and inflammatory nodules).

Studies have shown that HS is a neutrophil-driven disease, and that complement activation with the production of terminal fragment C5a may be important in the pathogenesis of the disease (Kanni et al, 2018). The C5a-C5aR signaling axis is essential in mediating neutrophil activation and migration. Recently it has been reported that circulating C5a and C5b-9 levels were significantly greater in HS patients, further adding to the relevance of C5a-C5aR an important mechanistic contributor to the disease process. More importantly, plasma from HS patients activates neutrophils (CD11b upregulation) ex vivo, and this activation can be blocked by a neutralizing antibody against C5a (IFX-1; Kanni T, et al. 2018), suggesting that C5a may be a critical factor in driving neutrophil activation and infiltration in the diseased tissue in HS patients. An anti-C5a agent, IFX-1, has shown efficacy in a Phase 2 study, suggesting a role for C5a blocking agents in the treatment of HS (Guo et al, 2017).

Avacopan, an orally administered, C5a receptor (C5aR) selective agent, was shown to be effective and safe in a Phase 2 study in subjects with AAV (Jayne et al, 2017) and is being tested in a Phase 3 clinical trial in subjects with AAV. Since HS is a neutrophil-driven disease and avacopan selectively blocks the C5aR, the activation of which leads to neutrophil attraction, avacopan has the potential to be an effective therapy for patients with HS. Hence, the clinical hypothesis of this trial is to test whether avacopan is effective in treating patients with moderate to severe HS.

This clinical trial will be conducted in compliance with the protocol, good clinical practice (GCP), and applicable regulatory requirements.

2. OBJECTIVES

2.1. Primary Objectives

The primary objectives of this study include:

1. Evaluation of the efficacy of avacopan compared to placebo in subjects with Hurley Stage II or III hidradenitis suppurativa (HS) based on subjects achieving a Hidradenitis Suppurativa Clinical Response (HiSCR) after 12 weeks of treatment. HiSCR is defined as at least a 50% reduction in abscess and inflammatory nodule count with no increase in abscess count and no increase in draining fistula count at Week 12 relative to baseline.
2. Evaluation of the safety of avacopan compared to placebo in these subjects based on the adverse event incidence, changes from baseline in laboratory parameters, and vital signs.

2.2. Secondary and Other Objectives

The secondary and other objectives of this study include:

1. Evaluation of the efficacy of avacopan compared to placebo in these subjects include:
 - a. The subject's global assessment of skin pain numeric rating scale (NRS),
 - b. The modified Sartorius score, and
 - c. Achieving an AN count of 0, 1, or 2.
2. Assessment of patient-reported outcomes including health-related quality-of-life changes based on the Short Form-36 version 2 (SF-36 v2), the EuroQOL-5D-5L (EQ-5D-5L), the

Hidradenitis Suppurativa Quality of Life (HiSQOL) Index, the Dermatology Life Quality Index (DLQI), and the Work Productivity and Activity Impairment Questionnaire: Specific Health Problem (WPAI:SHP) with avacopan compared to placebo.

3. Evaluation of the pharmacokinetic profile of avacopan in subjects with HS.
4. Evaluation of the safety and efficacy of avacopan treatment from Day 1 by each timepoint up to Week 44 in subjects with HS.
5. Evaluation of the efficacy of avacopan compared to placebo in these subjects include:
 - a. The Sartorius score, International HS Severity Scoring System (IHS4) score, HS Physician Global Assessment (HS-PGA),
 - b. Proportion of subjects who experienced flare, who experienced loss of response during Period 2, who received oral antibiotic rescue therapy or lesion intervention, and who received disallowed opioid pain therapy, and
 - c. The duration of flare in days.
6. Evaluation of health-economic information.

3. STUDY DESIGN

The study is a randomized, double-blind, placebo-controlled, three-group Phase 2 trial in approximately 390 subjects with moderate to severe hidradenitis suppurativa (Hurley Stage II or III). Subjects will be randomized 1:1:1 to a treatment of 10 mg avacopan twice daily, 30 mg avacopan twice daily or placebo for 12 weeks. Other systemic treatments for HS including anti-TNF- α treatments are prohibited. Stable antibiotic therapy with doxycycline or minocycline is allowed as specified in the protocol. Subjects treated with 10 mg or 30 mg twice daily during the blinded, placebo-controlled 12-week treatment period (Period 1) will be followed by an additional 24-week, active treatment period (Period 2) during which they will continue to receive the same dose regimen, either 10 mg or 30 mg avacopan twice daily. Subjects on placebo who complete Period 1 will be re-randomized 1:1 to receive 10 mg or 30 mg avacopan twice daily in Period 2. During Period 2 the treatment assignment to 10 mg or 30 mg twice daily will not be disclosed to the subject, study site personnel or the Sponsor. Thereafter, all subjects will be followed for 8 weeks without study drug before they exit the study.

To obtain balance across treatment groups, a stratified randomization scheme will be implemented. The stratification factors and strata within each factor are listed below.

3.1. Stratification and Randomization

1. Hurley Stage (Stage II vs. III)
 - a. Stage II disease: one or more widely separated recurrent abscesses with tract formation and scars, or
 - b. Stage III disease: multiple interconnected tracts and abscesses across an entire area, with diffuse or near diffuse involvement.
2. Concomitant antibiotic therapy (Yes vs. No)

- a. Concomitantly treated with doxycycline or minocycline as the only allowed antibiotic treatment for HS, or
 - b. No concomitant antibiotic therapy.
3. Anti-TNF- α treatment (Treatment naïve vs. Previous treatment):
- a. Did not previously receive anti-TNF- α drug such as adalimumab or infliximab (anti-TNF- α drug naïve), or
 - b. Previously (but no longer) received an anti-TNF- α drug and
 - completed anti-TNF- α treatment but may have relapsed, or
 - was intolerant to anti-TNF- α treatment, or
 - previously failed to respond or inadequately responded to anti-TNF- α treatment.

Not more than 20% of subjects will be in stratum 2a as described above.

Eligible subjects will be randomized with equal chance (i.e., 1:1:1) to one of the three treatment groups within each stratum based on a non-dynamic, list-based blocked randomization scheme.

- 1) Placebo twice daily
- 2) Avacopan 10 mg twice daily
- 3) Avacopan 30 mg twice daily

3.2. Study Treatments

Treatments for each group are shown in [Table 1](#).

The treatment period is 36 weeks (252 days), followed by an 8-week (56 days) follow-up period without taking study medication. Subjects will be randomized 1:1:1 to receive placebo, 10 mg avacopan or 30 mg avacopan b.i.d. for the blinded, placebo-controlled treatment for the first 12 weeks (Period 1). Subjects randomized to 10 mg and 30 mg avacopan in Period 1 will continue with the same drug regimen during the next 24-week active drug treatment period (Period 2). Subjects randomized to placebo in Period 1 will be re-randomized to receive either 10 mg or 30 mg avacopan b.i.d. in Period 2. Study treatment-group specific drug kits will be dispensed at relevant study visits. Detailed information about the study drug kits, dispensation and accountability is available in the Study Pharmacy Manual.

Study drug will be taken as described in [Section 5.2](#).

Table 1: Avacopan/Placebo Treatment for the Three Study Groups

	Period 1 (12-Week Placebo- Controlled Treatment)	Period 2 (24-Week Active Drug Treatment)
Group A Placebo	Kit # 1	Re-randomized 50% to Kit # 2 50% to Kit # 3
Group B 10 mg Avacopan	Kit # 2	Kit # 2
Group C 30 mg Avacopan	Kit # 3	Kit # 3

3.3. Study Flow

Subjects will be screened for eligibility based on the stage of the disease and their health status. The Screening period will be up to 28 days. The primary efficacy analysis can occur when the last enrolled subject has completed the Week 12 visit. After the blinded, placebo-controlled 12-week treatment period, all subjects will continue with a 24-week active treatment with 10 mg avacopan twice daily or 30 mg avacopan twice daily. After Week 36, all subjects will be followed for 8 weeks without receiving study medication.

All subjects will visit the study center during the 28-day Screening period, and, if eligible, on Day 1 and Weeks 2, 4, 8, 12, 16, 20, 24, 28, 32, 36, and 44 of the study. Study drug will be dispensed at the study site and subjects will take the first dose of study drug, i.e., avacopan or matching placebo, while at the study center. Preferably, on visit days subject should take their dose while on-site. Following the first dose, subjects will take study drug twice daily, which will continue for 12 weeks (84 days). Thereafter, all subjects will take avacopan study drug for 24 weeks (168 days), after which they will be followed for 8 weeks (56 days) without taking study drug. Study procedures at each visit day are detailed in the [Time and Events Table](#).

Subjects will exit the study when all the Study Week 44 visit procedures have been completed.

Subjects who experience a flare of HS during the study will be treated by the Investigator, which may include a maximum 1-week course of antibiotic rescue treatment with doxycycline or minocycline or intralesional Kenalog[®] rescue injections (triamcinolone acetonide, 10 mg total maximum per subject within a period no longer than 1 week). These subjects will be requested to remain in the study and to complete all study procedures if possible. During this time, subjects may continue to receive the study drug, if deemed clinically feasible by the Investigator.

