 - previously failed to respond or inadequately responded to anti-TNF- α treatment.

Not more than 20% of subjects will be in stratum 2a.

Subjects will be screened for eligibility based on the stage of the disease and their health status. The Screening period will be up to 28 days. The primary efficacy analysis can occur when the last enrolled subject has completed the Week 12 visit. After Period 1, all subjects will continue into Period 2 with an additional 24-week treatment with either 10 mg or 30 mg avacopan twice daily. The treatment assignment to 10 mg or 30 mg twice daily will not be disclosed to the subject, study site personnel or the Sponsor. Thereafter, all subjects will be followed for 8 weeks.

All subjects will visit the study center during the 28-day Screening period, and, if eligible, on Day 1 and Weeks 2, 4, 8, 12, 16, 20, 24, 28, 32, 36, and 44 of the study. Study drug will be dispensed at the study site and subjects will take the first dose of study drug, i.e., avacopan or matching placebo, while at the study center. Following the first dose, subjects will take study drug twice daily which will continue for 12 weeks (84 days). Thereafter, all subjects will take avacopan study drug for 24 weeks (168 days), after which all subjects will be followed for 8 weeks (56 days) without taking study medication. Study procedures at each visit day are detailed in the [Time and Events Table](#).

Subjects will be discontinued from the study when all the Study Week 44 visit procedures have been completed.

Subjects who experience a flare of HS or need HS lesion intervention during the study will be treated by the Investigator as outlined in [Section 5.7 Concomitant Therapy and Restrictions](#). These subjects will be requested to remain in the study and to complete all study procedures if

possible. During this time, subjects may continue to receive the study drug if deemed clinically feasible by the Investigator as described in [Section 5.7](#).

Discontinuation of study medication due to inadequate or worsening response in Period 2:

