5.7. Concomitant Therapy and Restrictions

No new treatment for HS (other than the study drug) may be introduced during the study period with the exceptions as outlined below.

All concomitant medications taken during the course of the study must be recorded meticulously on the concomitant medication pages in the EDC.

Anti- TNF- α Therapy, Systemic or Other Treatments with Potential Impact on HS:

Concomitant anti-TNF- α treatment during the trial is prohibited. Subjects who were previously treated with any anti-TNF- α drug and discontinued treatment >12 weeks prior to Day 1 visit would be allowed for enrollment.

Anti-TNF- α agents comprise five different FDA-approved drugs: adalimumab (Humira[®]), infliximab (Remicade[®]), entanercept (Enbrel[®]), golimumab (Simponi[®]), and certolizumab (Cimzia[®]). Of these anti-TNF- α agents, adalimumab, golimumab, and certolizumab share the longest mean terminal half-lives of 14 days as specified in their respective prescribing information labels. Subjects entering the trial need to be anti-TNF- α treatment-naïve or must have discontinued anti-TNF- α treatment for at least 12 weeks (which provides a washout period of over 5 times the half-life of any anti-TNF- α agent).

With the exception of permissible antibiotic treatment regimens, systemic or other treatments with a potential therapeutic impact on HS, including systemic antibiotic therapy, biologics and other systemic therapies such as methotrexate, cyclosporine, retinoids, and fumaric acid esters, etc., are prohibited.

Antibiotic Therapy: Concomitant use of oral antibiotic therapy for treatment of HS is generally not allowed. Systemic antibiotics (doxycycline or minocycline only) for the treatment of HS are permissible only for those subjects whose randomization was appropriately stratified for antibiotic use (see [Section 3.1 Stratification and Randomization](#)). During the study, the dose(s) of these drugs for the treatment of HS may not be increased. A systemic antibiotic must not be started for the treatment of HS during the course of the trial (treatment for a condition other than HS is allowed). However, the Investigators will be allowed to reduce the dose(s) or discontinue these ongoing antibiotic treatments during the study. Any dose changes in these treatments during the study must be recorded in the EDC system.

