Antibiotic rescue medication may be initiated at Week 4 or Week 8, if a subject experiences an increase in their AN count such that the total count is greater than or equal to 150% of their baseline AN count. For example, if a subject has a baseline (= Day 1) AN count of 15, antibiotic rescue therapy may be allowed with a minimum AN count of 23 ($1.5 \times 15 = 22.5$) at Week 4 or 8.

Subjects who qualify may initiate treatment with minocycline or doxycycline up to 100 mg b.i.d. The dosing regimen must remain stable throughout study participation. Rescue antibiotic therapy must be captured in the source document and on the appropriate eCRF.

Antiseptic Therapy: All subjects must use a topical antiseptic daily over the course of the study; topical antiseptics may include but are not limited to chlorhexidine, triclosan, benzoyl peroxide, or dilute bleach in bath water.

Wound Care: Concomitant use of wound care dressings on HS wounds is allowed.

Lesion Intervention: In the event that an acutely painful lesion occurs that requires an immediate intervention, physicians will have the option to perform protocol-allowed interventions. All study visit evaluations must occur before any interventions are performed. Any lesion that undergoes an intervention will be documented in the source. The site will be required to count any lesion that undergoes an intervention as permanently present from the date of the intervention, and must account for it in the source and on the appropriate eCRF.

Lesions that receive lesion interventions will be reported as adverse events.

Only two types of interventions are allowed: injection with intralesional triamcinolone acetonide suspension (intralesional Kenalog[®] rescue injections, i.e., triamcinolone acetonide, 10 mg total maximum per subject within a period no longer than 1 week) and incision and drainage.

If incision and drainage is performed, the required over-the-counter antiseptic wash should continue to be used. New systemic and topical therapies following incision and drainage (including antibiotics), are prohibited. Concomitant use of wound care dressings is allowed.

Subjects should continue using any allowed ongoing oral and topical therapies during the study.

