8.8. Statistical Analysis Methodology

8.8.1. General Approach

All study data will be summarized by treatment using descriptive statistics. Categorical variables will be reported as frequency and percent (e.g., gender, race). Continuous variables will be reported as number of subjects, mean, standard deviation, median, minimum, and maximum (e.g., age, weight). All summaries, statistical analyses, and individual subject data listings described below will be completed using Version 9.3 or later of the SAS Statistical Analysis System (SAS Institute, Inc. Cary, NC).

All statistical testing will be two-sided, with the Type I error rate at $\alpha = 0.05$.

Baseline is defined as the last value prior to start of dosing with study drug (typically the Day 1 pre-dose value).

Non-Responder Analysis: For non-responder analysis, the following imputation rules will be applied to categorical and continuous efficacy variables, respectively:

- Categorical Efficacy Variables: Non-Responder Imputation (NRI) will be used as the primary analysis. Last Observation Carried Forward (LOCF) will be the secondary approach for the non-responder analysis.
- Continuous Efficacy Variables: LOCF will be used as the primary analysis. The valid assessments from last visit prior to the visit the subject was considered a non-responder will be carried forward to the end of study for continuous efficacy variables. Baseline efficacy evaluations will not be carried forward.

The following are examples for subjects who will be counted as non-responder:

- Concomitant anti-TNF- α treatment or other treatments with clinically relevant impact on HS;
- Antibiotic rescue therapy;
- Non-protocol specified lesion intervention, or higher than permitted frequency or number of pre-specified lesion interventions. Protocol-specified lesion interventions will *not* be counted as Non-responder.

Concomitant therapy that would qualify a subject as non-responder will be reviewed prior to database lock. More details will be provided in the Statistical Analysis Plan (SAP).

Missing Data Analysis: For missing data analysis, the following imputation rules will be applied to categorical and continuous efficacy variables, respectively:

- Categorical Efficacy Variables: NRI will be the primary approach for categorical variables. The NRI analysis will count subjects who have missing values at a specific visit as non-responders for that visit. LOCF will be the secondary approach for the missing data analysis.

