The purpose of this document is to provide a description of the statistical methods and procedures to be implemented for the analysis of data from ChemoCentryx, Inc. Protocol CL016_168. This document is based on Protocol Amendment 2.0 (31JULY2019). If circumstances arise during the study such that more appropriate analytic procedures become available, the statistical analysis plan (SAP) may be revised. The statistical definitions and analytical methods described in this SAP supersede that in the protocol. Any revisions to the primary endpoint analyses and significant revisions to the secondary endpoint analyses will be made prior to the database freeze for the data in the double-blind treatment period through Week 12. Reasons for such revisions will be described in the final Clinical Study Report (CSR).

B. Protocol and Amendment History

This Statistical Analysis Plan (SAP) is based on 31JUL2019 of Protocol CL016_168, Amendment 2.0.

Version	Approval Date	
Original Protocol	19 October 2018	
Amendment 1	19 March 2019	
Amendment 2	31 July 2019	

II. Protocol Objectives

The study is a randomized, double-blind, placebo-controlled, three-group Phase 2 trial in approximately 390 subjects with moderate to severe hidradenitis suppurativa (Hurley Stage II or III). Subjects will be randomized 1:1:1 to a treatment of 10 mg avacopan twice daily, 30 mg avacopan twice daily or placebo for 12 weeks. Subjects treated with 10 mg or 30 mg twice daily during the blinded, placebo-controlled 12-week treatment period (Period 1, day 1 to week 12) will be followed by an additional 24-week, active treatment period (Period 2, week 12 to week 44) during which they will continue to receive the same dose regimen, either 10 mg or 30 mg avacopan twice daily.

A. Primary

1) Evaluation of the efficacy of avacopan compared to placebo in subjects with Hurley Stage II or III hidradenitis suppurativa (HS) based on subjects achieving a Hidradenitis Suppurativa Clinical Response (HiSCR) after 12 weeks of treatment. HiSCR is defined as at least a 50% reduction in abscess and inflammatory nodule (AN) count and no increase in abscess count and no increase in draining fistula count at Week 12 relative to baseline. Evaluation of the safety of avacopan compared to placebo in these subjects based on the adverse event incidence, changes from baseline in laboratory parameters, and vital signs

B. Secondary

- Evaluation of the efficacy of avacopan compared to placebo in these subjects include:

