 a. WPAI:SHP: Change from Baseline to each timepoint during Period 1 and Change from Week 12 to each timepoint during Period 2 and including the follow-up period; Work Productivity and Activity Impairment Questionnaire (WPAI:SHP) assesses the effect of general and specific health conditions on productivity losses. Scores are calculated for four areas: percent work time missed due to HS, percent impairment while working due to HS, percent overall work impairment due to HS, and percent activity impairment due to HS. Forms for this instrument will be completed by study subjects at visits specified in the Time and Events Table to measure changes from baseline in work productivity and activity impairment.

 Hospitalizations (cumulative) by period: Number of Hospitalizations total and due to HS, Number of days hospitalized, Number of days missed from work.

Hospitalizations are captured in Heath Economics Information CRFs, cumulative number will be calculated by sum of the numbers from each visit.

 Emergency or Urgent Care visits (cumulative) by period: Number of visits total and due to HS, Number of days (or hours where applicable) missed from work.

Emergency or Urgent Care visits are captured in Heath Economics Information CRFs, cumulative number will be calculated by sum of the numbers from each visit.

d. Lesion interventions for HS by period: Number of days (or hours where applicable) missed from work due to HS lesion interventions.

Lesion interventions for HS are captured in Heath Economics Information CRFs, cumulative number of days missed from work due to HS lesion interventions will be calculated by sum of the numbers from each visit.

C. General Approach

Lesions that received intervention (incision and drainage, or intralesional injection of corticosteroid) will be counted as permanently present from the date of the intervention.

In order to adjust for the impact of major protocol disallowed treatments on the results of the trial, efficacy assessments obtained after the start of major protocol disallowed treatments will be excluded from the analysis (unless otherwise specified). Subject will be counted as non-responders for the categorical variables and have their last observation carried forward for continuous variables.

Concomitant therapy that would qualify as a rescue medication will be reviewed prior to database lock.

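### Protocol 3.3 contradicts 5.7 on when antibiotics may be given for a flare, and SAP VIII.C no longer names antibiotic rescue as non-response in the primary analysis

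*Protocol*

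**What the plan says.** **What sites may prescribe.**

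- Protocol 3.3 (Study Flow) says that a flare during the study will be treated by the investigator, "which may include a maximum 1-week course of antibiotic rescue treatment with doxycycline or minocycline". It gives no visit, no AN threshold and no pointer to 5.7.
- Protocol 5.7 opens by saying that no new HS treatment other than study drug "may be introduced during the study period with the exceptions as outlined below". Under Antibiotic Therapy it adds: "A systemic antibiotic must not be started for the treatment of HS during the course of the trial". Its one rescue exception reads "Antibiotic rescue medication may be initiated at Week 4 or Week 8", and applies only when the AN count is at least 150% of baseline. The dose limit is 100 mg twice daily, and the regimen must then stay unchanged for the rest of participation.
- The Protocol Synopsis (Study Interventions/Methodology) sends the reader to 5.7: "Subjects who experience a flare of HS or need HS lesion intervention during the study will be treated by the Investigator as outlined in" that section.

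**How rescue is scored.**

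- Protocol 8.8.1 includes "Antibiotic rescue therapy" among its examples of non-response.
- SAP I.A says: "The statistical definitions and analytical methods described in this SAP supersede that in the protocol". SAP X presents the VIII.C wording as the updated non-responder definition.
- SAP VIII.C says that "efficacy assessments obtained after the start of major protocol disallowed treatments will be excluded from the analysis". Those subjects become non-responders for categorical variables and have LOCF for continuous ones. VIII.C says that rescue medication will be reviewed before lock, but not what follows from that review.
- SAP VI.J, in a parenthesis in the PP1 criteria, says that rescue allowed by the protocol leads to non-response or to LOCF.
- SAP VIII.D, sensitivity analysis 2, counts any add-on antibiotic before Week 12 as non-response, whatever the reason for use.

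**The concern.** Two gaps meet on the same event.

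First, sites have two incompatible instructions in current text. A one-week course at Week 2, or at Week 4 or 8 with AN below 150% of baseline, is permitted by 3.3 and barred by 5.7. The deviation class of such a course is then unclear. So is PP1 status: the subject is kept as a non-responder if the course is called allowed rescue, and removed if it is not.

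Second, the scoring rule in VIII.C turns on whether a treatment is disallowed. Rescue that meets 5.7 is allowed by definition, so the literal wording does not reach it. The observed Week 12 HiSCR would stand in the ITT1 primary analysis, against the intent of Protocol 8.8.1. The handling of an intercurrent event in the primary endpoint should not depend on a parenthesis in a per-protocol definition.

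**Working it through.** **1. The two conduct rules side by side**

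| | Protocol 3.3 | Protocol 5.7 |
|---|---|---|
| When | any flare during the study | Week 4 or Week 8 only |
| AN threshold | none | at least 150% of baseline |
| Duration | at most 1 week | stable throughout participation |

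The scheduled post-baseline visits before Week 12 are Weeks 2, 4 and 8, so for the primary endpoint 5.7 permits a start at 2 of 3.

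**2. The threshold gap.** Protocol 8.5.3 defines a flare as an AN rise of at least 25% and at least 2 lesions. For baseline b, a flare needs max(ceil(1.25b), b + 2) and 5.7 rescue needs ceil(1.5b).

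| Baseline AN | Flare | 5.7 rescue |
|---|---|---|
| 5 | 7 | 8 |
| 10 | 13 | 15 |
| 15 | 19 | 23 |
| 30 | 38 | 45 |

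The value 23 matches the worked example in 5.7 (1.5 × 15 = 22.5). A subject with baseline 15 and a count of 19 to 22 is in flare but does not qualify under 5.7.

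**3. HiSCR after 5.7 rescue.** AN must go from at least 1.5b to at most 0.5b: (1.5b − 0.5b)/1.5b = 66.7%. In whole lesions, baseline 5 means 8 to 2 (75%) and baseline 15 means 23 to 7 (70%). The time available is 85 − 29 = 56 days from Week 4, or 85 − 57 = 28 days from Week 8. This bound does not cover courses given under 3.3 alone, which has no threshold. From a 25% rise the required fall is (1.25 − 0.5)/1.25 = 60%.

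**4. The plan's own power.** Inputs from Protocol 8.3: 30% vs 50%, 130 per arm, two-sided 0.05. With pooled variance, power = Φ[(d − 1.96·√(2p̄(1 − p̄)/n)) / √((p₁q₁ + p₂q₂)/n)]. Here d = 0.20, the null standard error is √(0.48/130) = 0.0608 and the alternative is √(0.46/130) = 0.0595. This gives Φ(1.36) = 91.3%, which agrees with the stated figure of about 90%.

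**5. Size in ITT1, on assumed rates.** Take 30% (39/130) and 50% (65/130) as the rates with every rescued subject scored as a non-responder. Then let rescued subjects keep their observed response.

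- Low: 7 rescued on placebo and 3 on avacopan, 10% in HiSCR. (39 + 0.7)/130 = 30.5%; (65 + 0.3)/130 = 50.2%; difference 19.7 points; power 90.4%.
- High: 13 and 7 rescued, 30% in HiSCR. (39 + 3.9)/130 = 33.0%; (65 + 2.1)/130 = 51.6%; difference 18.6 points; power 86.4%.
- Equal numbers rescued and equal response after rescue in both arms: the difference stays at 20.0.
- Outer bracket: rescue in 5% to 20% of placebo and 2.5% to 10% of avacopan subjects, with up to 50% in HiSCR. The difference is 19.8 to 15.0 points and power 90.5% to 68%. The lower end needs half of the rescued subjects to reach HiSCR, which step 3 makes implausible for 5.7 rescue.

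**6. Size in PP1, on assumed counts.** Removing 2, 5 or 10 rescued non-responders per arm instead of keeping them gives 26/128 = 20.3, 26/125 = 20.8 or 26/120 = 21.7 points.

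**The case against.** The strongest reply is that both intentions can be recovered. The synopsis points to 5.7, and 5.7 is the specific rule with a worked example, so 3.3 reads as text that was not harmonised. On the SAP side, the PP1 parenthesis describes how the efficacy analysis treats allowed rescue, and nothing in the SAP says that rescued subjects keep their observed response. The pre-lock review sentence in VIII.C closely parallels the one on non-responders in Protocol 8.8.1, which suggests that rescue was still meant to lead to non-response. Sensitivity analysis 2 would show any effect.

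Most of this stands as evidence of intent. It does not remove the permission in 3.3, and it does not put the rule where ITT1 handling is defined. Sensitivity analysis 2 also counts antibiotics taken for other conditions, so it is not the 8.8.1 rule.

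Three stronger readings are tempting but unsupported:

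- **That the multiple-imputation step leaves out antibiotic rescue.** It forces non-response for anti-TNF and for other treatments with a relevant effect on HS. Protocol 8.8.1 lists rescue separately, but only as examples. Exclusion criterion 9 and 5.7 both count systemic antibiotics among treatments that may affect HS. The phrase is ambiguous and is not shown to exclude rescue.
- **That 5.7 permits a start at only 2 of 11 post-baseline visits.** This is true of the whole study, but 8 of those visits are at Week 12 or later. It overstates the gap for the primary endpoint.
- **That the ambiguity allows bias after unblinding.** PP1 status and the rescue review are both settled before lock, and PP1 status is also fixed before unblinding.

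**Conclusion.** The point holds as an internal inconsistency. Protocol 3.3 and 5.7 conflict in current text on timing, threshold and duration, and that part rests on no assumption. VIII.C omits antibiotic rescue from the non-response rule, and its literal reading departs from Protocol 8.8.1 for rescue that 5.7 allows. It would be too strong to say that the SAP has abandoned the rule, because the PP1 parenthesis still carries it.

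The effect on the Week 12 result is probably small. Under the assumed rates, the literal reading lowers the planning difference by 0.3 to 1.4 points and power from 91% to between 90% and 86%. The rescue counts and the response after rescue are assumptions, because the documents give neither. The sample size calculation is not in question. The case for correction is that the text governs what sites may prescribe and how a primary-endpoint event is scored.

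**What to change.** - **Protocol 3.3:** replace the antibiotic text with a cross-reference to 5.7, as the synopsis already does.
- **SAP VIII.C:** state that any rescue or add-on antibiotic for HS in Period 1, allowed or not, is non-response for binary variables and LOCF for continuous variables from its start date.
- **SAP VIII.D, multiple imputation:** for clarity, say that the forced non-responder category includes antibiotic rescue.
- **PP1:** classify each course against 5.7 in the pre-lock review that is already planned.

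The cost is one protocol clarification, one SAP sentence and one clause. Rescue therapy is already captured on the eCRF under 5.7, so no new data are needed. The SAP changes should be made before the Period 1 data are frozen, which is the limit that SAP I.A sets for revisions to the primary analysis.
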